### **Data Analysis to be reported in future publication**

Groups were compared on intake variables using Fisher’s exact tests for dichotomous variables, chi-square tests for categorical variables with more than two categories, and t-tests for continuous variables. Outcome measures were analyzed using generalized estimating equations (GEE) (Zeger, Liang, & Albert, 1988), including and excluding the stratification variables as covariates. GEE results presented use the covariate model unless otherwise specified. Planned comparison t-tests were used to compare between and within groups on outcome measures at time points 1 and 6. Analyses were intent-to-treat and conducted using SAS version 9.3. Missing data were treated as missing-missing. Analyses were two-tailed with statistical significance set at alpha of .05. Due to the error in the collection of biometric data, analyses for these variables are not included.

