### **Analytic plan for SteadyRx study**

Descriptive statistics (means and standard deviations or proportions) will be calculated for demographics, baseline participant factors (e.g., quality of life, substance use), treatment history, health literacy, and application ratings and engagement. All analyses will be intent to treat; all participants who are randomized will be included. All analyses will be adjusted for the pre-specified covariates used for stratification. All hypothesis tests will be two-sided,  $\alpha$  will be set at 0.05, and p-values for secondary analyses will be corrected to maintain  $\alpha=0.05$ . Based on our past research and the automated collection of our primary outcome measure, we expect relatively little missing data and little difference in the rates of missing data across groups. We plan to conduct analyses in which missing samples are assumed to represent the adverse outcome (e.g., missing = drug positive) and in which missing data will be ignored (missing = missing). The “missing positive” method is more conservative and will be considered the primary method.

Primary Outcomes. The effects of the intervention relative to the control group on the dichotomous monthly adherence measure will be analyzed with a longitudinal logistic regression model with treatment group and time as covariates. The group term, representing the between-group difference averaged over time, will be the primary coefficient of interest. Correlation among outcomes over time within individuals will be handled using the method of Generalized Estimating Equations (GEE). The dichotomous viral load variable (<400 HIV-RNA/mL, y/n) will be modeled with an analogous model but with only two follow-up measures.

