Secondary and Exploratory Analyses. Continuous measures assessed repeatedly over time (bottle openings, CD4, HIV-1 RNA, and MOS-HIV) will be analyzed using a longitudinal linear regression model, analogous to that used for the primary outcomes. We will control for baseline values in the CD4, viral load, and MOS-HIV models. Measures assessed only at intake will be analyzed via linear or logistic regression as appropriate. Baseline predictors of response to treatment, including positive urine screen for cocaine or opioids, health literacy (TOFHLA), depression (BDI), psychological factors (SCL-90), job and educational history (VEA), and executive function (Wisconsin Card Sorting) will be assessed by fitting regression models with interactions between treatment assignment and each predictor variable, to determine if the effect of treatment on outcome varies as a function of each of these predictors. Similar models, with an interaction between treatment group and drug use, adherence to buprenorphine/methadone, and attendance to primary care, respectively, (as time-varying covariates) will allow us to determine whether these variables affects response to treatment.

Usage, Acceptability, and Cost. Acceptability and SUMI global scale scores, app uses per day, daily duration of use, and cost of the app and incentives and ICER will be summarized via descriptive statistics (mean, SD, medians, histograms).

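### The publication analysis describes between- and within-group t-tests at time points 1 and 6 that the analytic plan does not list, with no correction stated and adjustment left unclear

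*Combined protocol and SAP*

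**What the plan says.** Two sections of the Combined protocol and SAP bear on this.

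*Analytic plan for SteadyRx study* fixes the primary test for the GEE models: "The group term, representing the between-group difference averaged over time, will be the primary coefficient of interest". It sets two general rules. On covariates: "All analyses will be adjusted for the pre-specified covariates used for stratification". On multiplicity: "p-values for secondary analyses will be corrected to maintain" an alpha of 0.05; neither the method nor the family is named. Under Secondary and Exploratory Analyses, repeated continuous measures "will be analyzed using a longitudinal linear regression model, analogous to that used for the primary outcomes". The section lists no t-test, no contrast at a single month and no within-group comparison.

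*Data Analysis to be reported in future publication* then states: "Planned comparison t-tests were used to compare between and within groups on outcome measures at time points 1 and 6". On covariates it says that GEE was run with and without the stratification variables and that "GEE results presented use the covariate model unless otherwise specified". On error control it says only: "Analyses were two-tailed with statistical significance set at alpha of .05". It also removes some outcomes: "Due to the error in the collection of biometric data, analyses for these variables are not included".

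**The concern.** A reader of the publication will take a planned comparison to be a pre-specified one, yet the only plan in the documents does not contain these tests. The publication section does not call them supportive or secondary, does not give their number, and does not mention the correction that the analytic plan promises. The covariate default does not reach them by its wording, and an ordinary two-sample or paired t-test carries no covariates.

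Two different things are at stake. The between-group tests give extra chances of a nominally significant group difference beside the primary test. The within-group tests invite the statement that one arm improved and the other did not, which is not a comparison of the arms.

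**Working it through.** **1. The texts side by side.**

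| | Analytic plan | Publication section |
|---|---|---|
| Group comparison | GEE group term, an average over the months | GEE, plus t-tests at time points 1 and 6 |
| Within-group comparison | none listed | t-tests |
| Covariates | all analyses adjusted | default stated for GEE results only |
| Secondary p-values | corrected | alpha .05, no correction stated |

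The documents give no power calculation or family-wise error rate, so there is no figure of the plan's own to reproduce. The figures below are illustrations.

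**2. Between-group tests.** Inputs: N = 50 in two groups (*Design*), taken as 25 per arm; six monthly assessments (*Collection Schedule*), with time points 1 and 6 read as months 1 and 6; two-sided 0.05. The within-person correlation is not given; 0 to 0.9 is assumed. There is no true group difference.

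- Bounds by hand: two independent tests give 1 − 0.95² = 0.0975; two perfectly correlated tests give 0.05.
- Simulation, 40,000 null trials per setting, normal outcome, at correlation 0 / 0.3 / 0.5 / 0.7 / 0.9: at least one of the two tests significant in 9.6 / 9.5 / 9.3 / 8.2 / 6.9% of trials.

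This is per outcome, and holds if the tests are adjusted or the covariates have no effect. If they are unadjusted and the covariates matter, the direction changes. *Randomization Variables* balances the arms on these covariates by an urn, so variation that they explain stays in the residual and widens the standard error. The main cost is then power, not extra false positives.

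**3. Within-group tests.** These are read as one paired test per arm, month 1 against month 6. Additive effects of fixed baseline covariates cancel in a paired difference, so the adjustment question concerns the between-group tests. Suppose both arms share a true change of d SD, with correlation ρ. Each paired test has 24 df and noncentrality d√25 / √(2(1 − ρ)). With p its power, exactly one arm is significant with probability 2p(1 − p).

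- d = 0.2, ρ = 0.3: noncentrality 1.0/√1.4 = 0.845; p = 0.128; 2p(1 − p) = 0.22.
- d = 0.4, ρ = 0.5: noncentrality 2.0/√1 = 2.0; p = 0.484; 2p(1 − p) = 0.50.
- d = 0.5, ρ = 0.7: noncentrality 2.5/√0.6 = 3.227; p = 0.872; 2p(1 − p) = 0.22.

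Over these assumed ranges the result is 22-50%, with no treatment effect at all.

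**4. What a correction costs.** A test with 80% power at 0.05 has noncentrality 1.960 + 0.842 = 2.802.

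- At 0.025: Φ(2.802 − 2.241) = 0.71.
- At 0.05/8 = 0.00625: Φ(2.802 − 2.734) = 0.53, or about 0.50 on a t reference with 48 df.

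The count of eight is an example. It assumes that the removed biometric variables are CD4 and HIV-1 RNA. MEMS and self-report percentages, each with one group term and two contrasts, make 6; two contrasts on the dichotomous adherence measure make 8.

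**The case against.** The best defence is that the analytic plan's rules are general. It covers all analyses for adjustment and all secondary p-values for correction, and nothing in the publication section withdraws this. That section is a short methods summary in the past tense, so its silence may be brevity. The t-tests could also be contrasts taken from the adjusted GEE. This stands in part: the documents do not show that the tests were unadjusted or uncorrected in fact. But compliance cannot be presumed, because the same section openly departs from the plan elsewhere: it treats missing data as missing, where the plan makes missing-as-adverse primary.

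Three stronger readings are tempting and are not supported.

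- *The tests were chosen after the data were seen.* Planned comparison is a usual term for contrasts fixed in advance. The documents do not show when these were chosen, so deleting the word is not justified; stating the timing is.
- *The false-positive rate for a treatment effect is 16-20%.* Adding the two paired tests to the two between-group tests gives 15.6-16.9% in the same simulation, and adding the group term gives 16.0-19.7%. These totals assume no time trend and count paired tests that do not compare the arms, so they are not rates of false treatment claims.
- *The GEE contrasts need a small-sample variance correction throughout.* For the dichotomous measure, simulated logistic GEE with 50 participants gave about 5% for the uncorrected robust test and about 3.5-4% with a Kauermann-Carroll correction, which is conservative. Any such correction would have to be limited to continuous outcomes.

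It is also fair that this is a pilot and that the primary test is untouched.

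**Conclusion.** The concern holds as a conflict between the two sections over additional tests. The publication section describes comparisons that the analytic plan does not list, states no correction although the plan requires one for secondary p-values, and leaves adjustment unclear although the plan requires it everywhere. It does not undermine the primary adherence analysis.

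The size is moderate: about 7-10% per continuous outcome for the two between-group tests instead of 5% for one, under the assumptions shown, and more across outcomes, whose number is not given. The within-group tests are the more misleading part, because one arm alone reaching significance is common under a shared change. This should be put right before publication.

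**What to change.** In *Data Analysis to be reported in future publication*:

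1. Keep the covariate-adjusted GEE group term as the only primary test for adherence.
2. State that the time-point 1 and 6 comparisons are not listed in the analytic plan, when they were chosen and how many were done, and label them secondary.
3. Take the between-group comparisons as covariate-adjusted contrasts from a separate GEE with categorical time and a group-by-time term, in line with the plan's adjustment rule.
4. Include them in the plan's correction of secondary p-values, for example Holm over all secondary tests reported, and name the method and the family.
5. Report within-group change as estimates with confidence intervals and no p-values.

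This costs some wording and one extra model per outcome; no new data are needed. The price is lower power for the single-month contrasts: 80% at 0.05 becomes about 71% at 0.025 and about 50-53% at 0.05/8, the first Holm step in the eight-test example.

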## Primary Outcome Variable

The primary outcome measures for intervention effectiveness will be (1) the percent of participants who take 95% of prescribed doses of their antiretroviral medication(s) within three hours of their scheduled dosing time each month as measured by MEMS, and (2) the percent of participants who achieve a viral load <400 HIV-RNA/mL at each of the two assessments collected during the active intervention period.

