## Secondary Outcome Variables

Secondary Measures. (1) Monthly percentage of on-time (i.e., within three hours of the scheduled time set by patient-physician agreement) bottle openings as measured by MEMS and self-report, respectively. Note that this is different from the primary measure which dichotomizes adherence (Y/N) with a 95% threshold. The primary measure is the measure of greatest clinical significance. The secondary measure is more sensitive to changes in behavior; (2) CD4 counts and HIV-1 RNA levels obtained at primary care visits.

Exploratory Measures. (1) MOS-HIV physical health and mental health summary scores (0-100) across the study period; (2) self-reported days of opiate and cocaine use.

Usage, Acceptability, and Cost Measures. Outcomes related to the usage and acceptability of the Smartphone application will include Acceptability Questionnaire total score, SUMI global scale score, average uses per day, and average duration of use per day. Outcomes related to the cost of the intervention will include total cost of the intervention per person, and the incremental cost-effectiveness ratio (ICER). To calculate ICER, we will divide the costs of the intervention by the difference between the two groups in terms of the percent of participants who take 95% of prescribed doses of their antiretroviral medication. The ICER can be interpreted as dollars spent per unit of desired outcomes gained. In addition, a more complete cost/benefit analysis conducted by academic economists will be included in a future large-scale study.

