**Elements of the monthly assessments.** The outreach coordinator will be responsible for:

- Attaching the MEMS reader to the assessment computer
- Obtaining CD4 and HIV-1 RNA levels from medical record
- Scheduling the next monthly assessment

**Reading a participant's MEMS cap.** Upon a participant's arrival, the outreach coordinator will place the MEMS cap on the reader and initiate the reading.

Tutorials for reading a MEMS cap will be made available to the outreach coordinator from the student investigators as well as from the help section located within the database. They will obtain CD4 and HIV-1 RNA levels from the medical record or from printed labs given by the participants. The outreach coordinator will inform WMU staff of the participant's arrival and any new lab information.

**Conducting Monthly Assessments.** The remainder of the monthly assessment will take place over the phone with one of the student investigators located in Kalamazoo. The student investigator is responsible for reading each assessment question aloud to the participant and filling in the answers accordingly. Upon the completion of both the MEMS reading and phone assessments, the participant should be paid \$50. If the participant brought in recent CD4 and RNA lab readings and have an undetectable viral load, they should be paid \$100, up to twice during the study. All relevant data logs should be updated (see [Monthly Assessment Checklist – WMU Staff](#)).

The student investigator is solely responsible for conducting the following assessments:

- [Visual Analog Scale for self-reporting ART adherence](#)
- [Medical Outcomes Study HIV Health Survey](#)
- [Addiction Severity Index-Lite](#)
- [Patient Reactions Assessment](#)

In addition to the previous assessments, student investigators are also responsible for conducting the following assessments for participants in the SteadyRx group:

- [SteadyRx Satisfaction Questionnaire](#)
- [Software Usability Measurement Inventory](#)

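### The publication analysis states only missing = missing, without reason or deviation label, although the analytic plan makes missing = adverse outcome the primary method

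*Combined protocol and SAP*

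**What the plan says.** The *Analytic plan for SteadyRx study* describes two ways of handling missing data. In the first, "missing samples are assumed to represent the adverse outcome (e.g., missing = drug positive". In the second, missing data are ignored. The plan ranks them: the first "method is more conservative and will be considered the primary method". It also states an expectation: "we expect relatively little missing data and little difference in the rates of missing data across groups".

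*Data Analysis to be reported in future publication*, written in the past tense, has one sentence on the subject: "Missing data were treated as missing-missing". It does not mention the other analysis. The same section does explain a different omission: "Due to the error in the collection of biometric data, analyses for these variables are not included". It also says that models were fitted with and without the stratification covariates, and which of the two is presented.

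*Primary Outcome Variable* names two primary outcomes: monthly attainment of the 95% on-time dosing threshold by MEMS, and "the percent of participants who achieve a viral load <400 HIV-RNA/mL at each of the two assessments".

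**The concern.** The two sections give different rules for the main analysis, and nothing else in the document reconciles them. The publication section is not an amendment log, so the difference cannot be set aside as superseded text. A reader of the publication would see only the lower-ranked analysis and could not tell whether the planned primary one agrees with it. The choice between two pre-specified rules would also look open to having been made after the results were known.

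The issue is sharpest for the dichotomous MEMS outcome, where counting a missing month as a failure is straightforward. If biometric data includes viral load, which is the natural reading but is not defined, MEMS adherence is the only primary outcome left.

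The plan bases its expectation of little missing data partly on automated collection. Retrieval is not fully automatic, however. Under *Monthly Assessments*, when the participant arrives, "the outreach coordinator will place the MEMS cap on the reader and initiate the reading". The data therefore still depend on the participant attending with the cap. This does not show that much is missing, but it is a reason to report how much.

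**Working it through.** **Text comparison.**

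| | Analytic plan | Publication section |
|---|---|---|
| Missing = adverse outcome | Planned, primary | Not mentioned |
| Missing = missing | Planned, not primary | The only rule stated |
| Reason for a change | – | None given |
| Labelled a deviation | – | No |

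**Size.** The documents contain no figure to reproduce: they give no adherence rate, no missing rate and no missingness by arm. All rates below are assumptions.

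Let p be the proportion of observed months that are adherent in an arm and m the proportion of months missing. C is control and T is SteadyRx.

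- Missing = missing: arm rate = p.
- Missing = adverse: arm rate = p(1 − m).
- Adverse-rule difference minus missing = missing difference = pC·mC − pT·mT.

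With pC = 0.40 and pT = 0.60, missing = missing gives 0.60 − 0.40 = 0.20 and OR = (0.60/0.40)/(0.40/0.60) = 2.25, whatever m is. The adverse-outcome rule gives:

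| Missing, C / T | Rate C | Rate T | Difference | OR |
|---|---|---|---|---|
| 5% / 5% | 0.40 × 0.95 = 0.38 | 0.60 × 0.95 = 0.57 | +19 points | 2.16 |
| 10% / 10% | 0.40 × 0.90 = 0.36 | 0.60 × 0.90 = 0.54 | +18 points | 2.09 |
| 10% / 20% | 0.40 × 0.90 = 0.36 | 0.60 × 0.80 = 0.48 | +12 points | 1.64 |
| 20% / 10% | 0.40 × 0.80 = 0.32 | 0.60 × 0.90 = 0.54 | +22 points | 2.49 |

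The first two rows match the plan's own expectation of little, balanced missingness, and the shift there is 1 to 2 points. The last two rows show that unequal missingness can move the estimate either way.

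**Neither rule is safe in general.** With no effect among observed months (40% in both arms), missingness of 20% / 10% gives 0.32 vs 0.36 under the adverse rule, a difference of +4 points. Reversing the missingness gives −4. Missing = missing gives 0 in both cases.

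Conversely, take true rates of 40% and 60%, and suppose control loses 20% and SteadyRx 10% of non-adherent months only. Missing = missing then gives 0.40/(0.40 + 0.60 × 0.80) = 0.455 vs 0.60/(0.60 + 0.40 × 0.90) = 0.625, which is +17 points and OR 2.00 instead of +20 and 2.25. The adverse rule is right in this example by construction, so the example is not evidence for that rule.

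**Leverage of one participant.** *Design* gives N = 50, and *Monthly Assessments* gives six assessments. Assuming 25 per arm, a participant with no MEMS data accounts for 6/(25 × 6) = 4% of the arm's months. Under the adverse rule this lowers the arm rate by 0.04 × 0.40 = 1.6 points or 0.04 × 0.60 = 2.4 points. Under missing = missing, that participant contributes nothing to the adherence GEE, although the plan requires every randomized participant to be analysed.

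**The case against.** The strongest reply is that missing = missing was also pre-specified, may be the better method, and under the plan's own expectation would barely differ from the other rule. All of that may be true. It does not remove the need to say that the ranking changed, why, and when.

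Several further limits stand:

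- The publication section refers to outcome measures in general and does not say that its GEE uses the dichotomous MEMS outcome. Its comparisons by t-test at time points 1 and 6 suit continuous measures, and for those the plan defines no adverse value.
- Even for MEMS, the plan's only example of the adverse value is drug-test language. Non-adherent is the natural reading but is not written down.
- *Monthly Assessments* provides for no-show calls, rescheduling, visits to the participant's residence and payment for bringing the bottle, all of which should limit missing readings.

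A reader might infer that the planned primary analysis was never run, that the rule was switched after results were seen, or that the switch favours SteadyRx. The documents support none of these. Silence about an analysis does not show that it was not done, no timing is given, and without missingness by arm no direction can be stated.

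A reader might also carry the effect into the incremental cost-effectiveness ratio, whose denominator is the "difference between the two groups in terms of the percent of participants who take 95% of prescribed doses of their antiretroviral medication". The publication section mentions no such ratio, and that denominator is not clearly the average monthly difference, so no multiplier can be attached to it.

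**Conclusion.** The concern holds as an undisclosed departure from the plan's primary missing-data rule, and it should be fixed. The mismatch in the text is certain. Its numerical effect is unknown: about 1 to 2 points if missingness is 5% to 10% and balanced, and in the illustrations with a 10-point imbalance the 20-point difference becomes 12 or 22. These figures rest on assumed observed adherence of 40% and 60% and on assumed missing rates. Relevance to a primary outcome rests on the published GEE covering dichotomous MEMS adherence. The statement that this is the only primary outcome left rests further on biometric data including viral load. No bias in the published result is shown.

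**What to change.** Amend *Data Analysis to be reported in future publication* and leave the analytic plan as the pre-specified record.

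1. Report the dichotomous MEMS adherence GEE under both planned rules, and identify missing = adverse outcome as the plan's primary method. State that coding a missing month as non-adherent is an interpretation made after the plan, because the plan does not define the adverse value for MEMS. If missing = missing stays as the headline, label it a deviation, give the reason, and say whether it was decided before results by arm were seen.
2. Report missing person-months by arm and the number of randomized participants with no MEMS data.

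The cost is a few sentences, one small table and one or two further GEE runs on existing data. The downside is a less tidy headline if the two results differ.
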